3.2.3 Blinding

Follow-up assessments will be conducted by research staff who are blind to which arm participants were randomized.

6.2.4 Follow-up Visits

For the purposes of targeting dates for monthly follow-up assessments, we will consider each month = 28 days (4 weeks exactly). For all follow-up assessments, research staff will make every effort to conduct the assessment within one week before or one week after the exact due date of the assessment. However, because all data can be analyzed with modern statistical methods regardless of whether it was collected inside that window, RAs will still collect data if possible even if it is later than that window. We will record the optimum date for the assessment (e.g., Enrollment + 84 days for M3 Protocol Version 2.8

assessment) as well as the actual date of the assessment. Follow-up visits will typically be conducted via a secure video-based platform, telephone and a REDCap link, or via telephone only (if participant does not have access to a computer/ smartphone, e.g., pre-randomization, or at M6 or M12 follow-up). If allowed by site policies, we may conduct follow-up visits in person with COVID precautions.

Similarly, for assessment of personal yoga practice (Weekly Yoga Journal), research staff will make every effort to conduct the assessment on a weekly basis (starting seven days from the date of randomization). However, because the Weekly Yoga Journal uses a time-line follow-up method, data from any missed weeks will still be collected during the next weekly or monthly assessment that is completed with the participant.

Staff at Butler Hospital or BMC may conduct follow-up visits.

Phase 1 and Phase 2 Visits:

- Weekly for 12 weeks
 - Study classes/groups
 - Weekly Yoga Journal
 - Injuries due to yoga
 - CEQ (after initial class only)
 - Any other AEs reported to RAs
 - Payment: \$5 – for completion of the Weekly Yoga Journal (if completed within window (due date + 6 days). Payment is provided in a lump sum at the end of the month.
- Month 1
 - Any other AEs reported to RAs
 - TSK
 - Self-efficacy for exercise
 - Logistic Factors
 - BREQ-2
 - BPI
 - NRS
 - ASI
 - McHugh Opioid Craving Scale
 - Payment: \$20
- Month 2
 - Any other AEs reported to RAs
 - TSK
 - Self-efficacy for exercise
 - Logistic Factors
 - BREQ-2
 - BPI
 - NRS
 - ASI
 - McHugh Opioid Scale
 - Payment: \$20

- Month 3 (Final evaluation for Phase 1)
 - Any other AEs reported to RAs
 - TRAQ
 - TSK
 - Self-efficacy for exercise
 - Logistic Factors
 - BREQ-2
 - BPI
 - NRS
 - WHOQOL-BREF
 - PROMIS® Depression Scale
 - PROMIS® Anxiety Scale
 - ASI
 - McHugh Opioid Scale
 - Pain Treatment Use
 - SAFTEE
 - Chart Review
 - Qualitative Exit Interview-- Study Procedures (Phase 1—long version; Phase 2 – short version)
 - Qualitative Exit Interview – Intersectional Stigma (All participants Phase 1; select participants Phase 2)
 - Payment: \$30 for the overall assessment. Participants who complete the entire assessment will be entered into a lottery to receive a \$100 bonus incentive (paid via giftcards or Clincard, depending on site). Participants may receive an additional \$20 if they complete the Qualitative Exit Interview—Intersectional Stigma.

Phase 2 Visits Only:

- Month 6
 - Weekly Yoga Journal
 - Injuries due to yoga
 - Any other AEs reported to RAs
 - TRAQ
 - BPI
 - NRS
 - WHOQOL-BREF
 - PROMIS® Depression Scale
 - PROMIS® Anxiety Scale
 - ASI
 - McHugh Opioid Craving Scale
 - Payment: \$30. Participants who complete the entire assessment will be entered into a lottery to receive a \$100 bonus incentive (paid via giftcards or Clincard, depending on site).
- Month 9
 - Weekly Yoga Journal
 - Injuries due to yoga

- Any other AEs reported to RAs
- Payment: \$20
- Month 12 (Final evaluation for Phase 2)
 - Weekly Yoga Journal
 - Injuries due to yoga
 - Any other AEs reported to RAs
 - TRAQ
 - BPI
 - NRS
 - WHOQOL-BREF
 - PROMIS® Depression Scale
 - PROMIS® Anxiety Scale
 - ASI
 - McHugh Opioid Craving Scale
 - Chart Review
 - Qualitative Exit Interview-- Study Procedures (Phase 2 – short version)
 - Payment: \$40. Participants who complete the entire assessment will be entered into a lottery to receive a \$100 bonus incentive (paid via giftcards or Clincard, depending on site).

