2. Modified our study cellphone procedures: Instead of requiring participants to return their phone to study personnel at the end of their first twelve weeks, the data plan for that phone will be canceled and participants will be allowed to keep the phone. We therefore removed the \$35 compensation for returning the study cell phone.
3. Removed Logistic Barriers measure from BL assessment. This measure asks about current barriers to yoga practice, and since participants will not have started the yoga intervention and are excluded if they have a yoga practice at BL screening, it does not make sense to ask about barriers at this time point.
4. Added \$20 compensation for participants who complete the M9 assessment
5. Added a brief qualitative exit interview for participants who withdraw from the study, along with \$20 compensation for those who complete the interview.

Version Number 2.4

Version Date: 5/5/23

Summary of revisions:

1. Updated the Study Team Roster:
 - a. Changed [name] from Site PI to Co-I, and added [name] as the new Site PI for Boston Medical Center
2. Updated who can be approached for the Phase 2 intersectional stigma interviews
3. Added a newsletter option
4. Specified that we may recruit more than one participant advisor per site per year
5. Included a raffle as an extra incentive for completing follow-up assessments.

Version Number 2.5

Version Date: 7/18/23

Summary of revisions:

1. Updated the Study Team Roster:
 - a. Added [name] as the new Site PI for Boston Medical Center
 - b. Specified under Informed Consent Procedures that for verbal consents and paper consents signed in-person, an audio recording or scanned copy of the consent (respectively) is stored in Box as documentation.

Version Number 2.6

Version date: 10/20/2023

Summary or revisions:

1. Clarified options by which participant may verify their buprenorphine or methadone prescription.
2. Removed [name] as a co-Investigator.

Version Number 2.7

Version Date: 12/13/23

Summary of Revisions:

1. Clarified the 3 main study sites (i.e., where research staff are located) as Butler Hospital, Boston Medical Center, and the Cleveland Clinic.
2. Clarified Cleveland Clinic as being responsible for screening and consenting, only.
3. Removed [name] as Coordinator and replaced with [name].
4. Clarified that self-report versions of follow-up surveys may be sent via email OR text.

Version Number 2.8

Version Date: 1/18/24

Summary of Revisions:

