6. STUDY PROCEDURES

6.1 Schedule of Evaluations

Table 1: Assessment schedule for Phase 1 and Phase 2

Assessment	Screening	Informed Consent Form	Baseline Visit 1	Baseline Visit 2	After initial class	Weekly during M1, M2, M3	M1 visit	M2 visit	M3 visit	M6 visit (Phase 2 only)	Month 9 call (Phase 2 only)	M12 visit (Phase 2 only)	Withdrawal
Inclusion/Exclusion	X		X										
Informed Consent Form		X ⁶											
Enrollment and Randomization				X									
Credibility Expectancy Questionnaire (CEQ)					X								
Weekly Yoga Journal						X				X	X	X	
Injuries due to yoga						X				X	X	X	
Systematic Assessment for Treatment Emergent Events (SAFTEE)										X			
Chart Review ¹			X ²							X ²			X ²
Other Adverse Events			X			X	X	X	X	X			X
SUD, psychiatric, sleep, and pain medications (modified TRAQ)			X							X	X		X
Tampa Scale of Kinesiophobia (TSK)			X				X	X	X				
Self-efficacy for exercise			X				X	X	X				
Logistic Factors							X	X	X				

Assessment	Screening	Informed Consent Form	Baseline Visit 1	Baseline Visit 2	After initial class	Weekly during M1, M2, M3	M1 visit	M2 visit	M3 visit	M6 visit (Phase 2 only)	Month 9 call (Phase 2 only)	M12 visit (Phase 2 only)	Withdrawal
Behavioral Regulation in Exercise Questionnaire (BREQ-2), modified for yoga							X	X	X				
Brief Pain Inventory (BPI) ³			X				X	X	X	X		X	
Numerical Rating Scale (NRS), Pain Severity			X				X	X	X	X		X	
WHO Quality of Life, Brief Version (WHOQOL-BREF)			X						X	X		X	
PROMIS Depression Scale			X						X	X		X	
PROMIS Anxiety Scale			X						X	X		X	
Addiction Severity Index (ASI)			X				X	X	X	X		X	
McHugh Opioid Craving Scale			X				X	X	X	X		X	
Demographics			X										
Review of Medical Comorbidities			X										
Pain Treatment Use			X						X				
Qualitative Exit Interview – Study Procedures (Phase 1: long version; Phase 2: short version)									X			X	
Qualitative Exit Interview-- Intersectional Stigma (Phase 2 only)									X ⁴				
Qualitative Exit Interview-- Study Feedback & Reasons for Withdrawal (Phase 2 only) ⁷													X

Assessment	Screening	Informed Consent Form	Baseline Visit 1	Baseline Visit 2	After initial class	Weekly during M1, M2, M3	M1 visit	M2 visit	M3 visit	M6 visit (Phase 2 only)	Month 9 call (Phase 2 only)	M12 visit (Phase 2 only)	Withdrawal
Payment		\$10	\$10			\$5 for each weekly assmt ⁵	\$20	\$20	\$30 (overall assessment) \$20 (Phase 2 qualitative exit interview, if conducted)	\$30	\$20	\$40	\$20

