⁵This will be paid at the end of each month. Only assessments that are completed within the assessment window (i.e., due date + 6 days) will be compensated.

⁶In order to maximize flexibility for the participant, informed consent may take place at the end of the initial screening, as its own appointment between screening and BL, or at the start of the BL assessment.

⁷The column furthest to the right (“Withdrawal”) may occur at any point between the Baseline Visit 2 and M12, following a participant’s withdrawal from the study intervention, assessments, and/or other study procedures.

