6.2.5 Completion/Final Evaluation

Even if participants drop out of study treatment, we will attempt to collect data at all assessment points if participants agree to it.

6.2.6. Procedures for re-contacting Phase 1 participants to participate in the Qualitative Interview—Intersectional Stigma.

First, study staff will review a participant’s Phase 1 materials, and contact participants only by methods that they originally agreed to be acceptable to them. Participants who did not complete the post-program (M3) assessment will not be recontacted. Next, research staff with whom participants had regular contact during the parent trial will contact participants via their preferred contact method(s) to briefly share information about the sub-project, as follows:

“Hi, this is [RA]. We are writing/ calling to see if you are interested in doing an additional interview for the yoga research program you were in. We want to ask you more about topics related to the research. We would pay you for the interview. Please respond if you would like to hear more about this.”

Participants will be contacted by research staff. Those responding attesting their interest will be provided more information about the study purpose and incentive details. The study RA will conduct an audio recorded oral consent process for this additional interview, and document oral consent. The audio-recorded consent will then be saved in a secure location, consistent with the parent study procedures. The research staff member will then coordinate scheduling with the interviewer.

We have completed a request for a Waiver of Authorization for use of PHI (attached) in order to be able to recontact participants.

Nature of the interview: This qualitative interview will include questions about participants’ pain, experiences of the yoga program, substance use, health behaviors (like eating and exercise), adverse interpersonal experiences experienced (like discrimination, teasing, bullying, unfair treatment,

or other experiences of victimization), and how participants cope with, manage, and/or find resiliency through such experiences. The interviewer will query participant perceptions of how yoga or related practices may have helped people cope with experiences of stigma, and perceptions of how yoga may be tailored to help people cope with such experiences.

6.2.7. Procedures for re-contacting Phase 2 participants to participate in the Qualitative Interview—Intersectional Stigma.

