9.5 Outcomes

9.5.1 Primary/Proximal Outcome

Phase 1 is a pilot study to assess feasibility. The primary aims and outcome assessments are shown in Table 4 below.

Table 4. Targets for Phase 1 Pilot Study.		
Feasibility Area	Method of assessment	Target at each site
Recruit participants	Number recruited per month	Recruit 10 participants in 4 months.
Train yoga teachers to fidelity	Teacher fidelity scale	Each teacher demonstrates >80% fidelity on final 3 classes rated.
Randomize participants to intervention components and correctly administer these components	Randomization errors; receipt of incorrect intervention components	No errors/ incorrect components received in 2 nd half of participants randomized.
Collect follow-up assessments	Percent of follow-up assessments collected (for M1, M2, and M3)	≥ 70% with sufficient data collected on dosage; ≥ 70% of other follow-up assessments collected, including chart reviews

The proximal outcome of Phase 2 is yoga dosage received. This will be calculated by adding the total number of minutes per week in the study yoga class and total number of minutes per week in personal practice (or outside yoga classes). Research staff will take attendance at study yoga classes, and, in the event someone does not attend the entire yoga class, will record the number of minutes present in class. We will measure personal practice using the Weekly Yoga Journal.

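### The paid withdrawal contact omits the Weekly Yoga Journal, so uncollected practice weeks before an early withdrawal from assessments are imputed rather than asked about

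*Combined protocol and SAP*

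**What the plan says.** Section 9.5.1 defines yoga dosage as weekly minutes in the study class plus weekly minutes of personal practice or outside classes. Staff record class minutes from attendance. For the other part it states: "We will measure personal practice using the Weekly Yoga Journal".

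Section 6.2.4 describes the Journal as a weekly instrument with a follow-back design. When a week is missed, "data from any missed weeks will still be collected during the next weekly or monthly assessment that is completed with the participant". No other recovery route is given.

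Table 1 in section 6.1 has a Withdrawal column with a $20 payment and a Phase 2 exit interview on study feedback and reasons for leaving. Footnote 7 allows this contact at any point from Baseline Visit 2 to M12, "following a participant’s withdrawal from the study intervention, assessments, and/or other study procedures". The "Weekly Yoga Journal" row is marked for the weekly assessments, M6, Month 9 and M12, and its Withdrawal cell is empty.

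For people who leave treatment but not assessments, section 6.2.5 says: "Even if participants drop out of study treatment, we will attempt to collect data at all assessment points if participants agree to it". Section 8 says much the same. Section 9.6 assumes that data are missing at random and uses multiple imputation by chained equations.

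**The concern.** The recovery rule presupposes a later weekly or monthly assessment. Someone who withdraws from assessments has none. The plan nevertheless expects to reach some of these people and to pay them for an interview. At that contact it holds an instrument designed to recover missed weeks, and it asks why the person left but not how much they practised.

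The weeks at stake come from people who are leaving the study, for whom missing at random is least secure. They also concern the part of dosage that the practice videos and the text messages are meant to raise. Dosage is the outcome on which Step 1 of section 9.6 screens components, so an observed value is preferable to an imputed one where it can be had at little cost.

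**Working it through.** **1. Is the Journal really absent from the withdrawal contact?**
- The Journal row of Table 1 has four marks. The visit lists in section 6.2.4 give the Journal at four kinds of time point: weekly for 12 weeks, Month 6, Month 9 and Month 12. Every mark is accounted for, so none belongs to Withdrawal.
- Section 6.2.4 has no withdrawal visit, and no other section gives the Journal there.
- Some other rows of Table 1 (SAFTEE, chart review, medications) appear one column out of line with the 6.2.4 lists in the extracted text. I draw nothing from their marks in the last column.

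**2. Who is affected?**

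| Participant | Later assessment? | Missed weeks recoverable under 6.2.4? |
|---|---|---|
| Leaves the intervention only | Yes, if they agree (6.2.5, section 8) | Yes |
| Leaves assessments, declines the exit contact | No | No, and the fix does not help |
| Leaves assessments, accepts the exit contact | No | No, but the contact could collect them |

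Only the third row is at issue, and only for weeks between the last completed Journal and withdrawal.

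**3. The plan's own figure.** Section 9.2 assumes about 17% attrition on dosage and powers for 192 − 34 = 158, or 79 per level of each component. It claims power above .80 for d = .40 and above .90 for d = .50. With power ≈ Φ(d√N/2 − z) and two-sided alpha .10 (z = 1.645):
- d = .40: .40 × √158 / 2 = 2.514; 2.514 − 1.645 = 0.869; power 0.808.
- d = .50: .50 × √158 / 2 = 3.142; 3.142 − 1.645 = 1.497; power 0.933.

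Both claims reproduce. Reading the plan's alpha/2 = .10 literally (two-sided .20) gives 0.891 and 0.969, which also meet the bounds.

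**4. Ceiling on the recoverable weeks.** Section 9.5.1 does not name the weeks over which dosage is counted. I take the 12-week intervention period, so 192 × 12 = 2,304 person-weeks. The documents give neither the number of withdrawals from assessments nor the number of uncollected weeks. Assume 2 to 4 uncollected weeks per person:
- All 34 reached: 34 × 2 = 68 and 34 × 4 = 136; 68/2,304 = 3.0% and 136/2,304 = 5.9%.
- Half (17) reached: 34 and 68 person-weeks, or 1.5% and 3.0%.
- None reached: 0%.

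**5. Bound on power.** If the extra weeks somehow made 0, 17 or all 34 lost participants fully analysable, N would be 158, 175 or 192. Power for d = .40 would then be 0.808, 0.842 or 0.870. The true gain must be smaller, because only weeks before withdrawal are recoverable.

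**The case against.** The strongest reply is that the affected group is narrow. A person must withdraw from assessments, still accept a paid interview, have uncollected weeks, and agree to give outcome data after declining assessments. The plan already limits the backlog: the Journal is attempted weekly with a $5 payment, an online version may be sent when repeated interview attempts fail (section 6.2), and late data are accepted. Keeping the exit contact short and qualitative is defensible. All of this stands, and it is why the size may be near zero. It does not remove the gap, because none of these measures operates once someone has left assessments.

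A second reply is that the remedy carries a risk. Follow-up assessors are to be blind to assignment (the Blinding section, listed as 6.2.3 in the contents). The documents do not say whether the exit interviewer is blind, and footnote 7 sets no limit on the delay after withdrawal, so recall could be long. This also stands and shapes the fix.

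A reader might infer several stronger things that the documents do not support:
- That half of the outcome is at stake. Section 9.5.1 adds two sources but gives no split of minutes.
- That all of the assumed attrition is recoverable. Section 9.2 does not equate attrition with formal withdrawal, and some lost participants may never be reached.
- That people typically skip journals before withdrawing. The plan does not say so.
- That injuries go unrecorded because that row of Table 1 is also empty at Withdrawal. Sections 7.1 and 7.3 ask about injuries at each class attended and take adverse-event reports at any time.

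**Conclusion.** The gap holds on the text. For participants who withdraw from assessments in the first 12 weeks and accept the paid exit contact, uncollected personal-practice weeks before withdrawal are left to imputation although the study could ask about them. Class minutes are not affected.

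The size cannot be computed from the documents. It lies between near zero and a ceiling of about 3.0% to 5.9% of person-weeks. That ceiling rests on all 34 assumed losses being reached with 2 to 4 uncollected weeks each, and on a 12-week outcome window.

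This is a point about avoidable, possibly informative missing data, not about power, since the stated power reproduces and does not depend on it. Nor would the change cure missingness from disengagement: weeks from withdrawal to week 12 would still be imputed under the same assumption. It is a modest improvement worth making because it is cheap.

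**What to change.** - In Table 1, mark the Weekly Yoga Journal in the Withdrawal column, with a footnote limiting it to withdrawals within the first 12 weeks.
- In section 6.2.4, widen the recovery rule so that missed weeks may be collected at the next weekly, monthly or withdrawal contact.
- State that, with the participant's agreement, the Journal is given by timeline follow-back from the last completed journal to the withdrawal date, before the exit interview. A blinded research assistant should give it, or the existing REDCap self-report version should be used.
- Flag these weeks as recalled at withdrawal, so that an analysis can be run with and without them.

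The cost is a short amendment and a few extra minutes at a contact that is already paid. The downsides are possibly longer recall, which the flag makes visible, and the need to arrange a blinded collector or the online form. Adding the injuries question at the same contact is optional and is not part of the case for this change.

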6.2.5 Completion/Final Evaluation

Even if participants drop out of study treatment, we will attempt to collect data at all assessment points if participants agree to it.

6.2.6. Procedures for re-contacting Phase 1 participants to participate in the Qualitative Interview—Intersectional Stigma.

First, study staff will review a participant’s Phase 1 materials, and contact participants only by methods that they originally agreed to be acceptable to them. Participants who did not complete the post-program (M3) assessment will not be recontacted. Next, research staff with whom participants had regular contact during the parent trial will contact participants via their preferred contact method(s) to briefly share information about the sub-project, as follows:

“Hi, this is [RA]. We are writing/ calling to see if you are interested in doing an additional interview for the yoga research program you were in. We want to ask you more about topics related to the research. We would pay you for the interview. Please respond if you would like to hear more about this.”

Participants will be contacted by research staff. Those responding attesting their interest will be provided more information about the study purpose and incentive details. The study RA will conduct an audio recorded oral consent process for this additional interview, and document oral consent. The audio-recorded consent will then be saved in a secure location, consistent with the parent study procedures. The research staff member will then coordinate scheduling with the interviewer.

We have completed a request for a Waiver of Authorization for use of PHI (attached) in order to be able to recontact participants.

Nature of the interview: This qualitative interview will include questions about participants’ pain, experiences of the yoga program, substance use, health behaviors (like eating and exercise), adverse interpersonal experiences experienced (like discrimination, teasing, bullying, unfair treatment,

or other experiences of victimization), and how participants cope with, manage, and/or find resiliency through such experiences. The interviewer will query participant perceptions of how yoga or related practices may have helped people cope with experiences of stigma, and perceptions of how yoga may be tailored to help people cope with such experiences.

6.2.7. Procedures for re-contacting Phase 2 participants to participate in the Qualitative Interview—Intersectional Stigma.

In order to give all participants the same opportunity to take part in this additional interview, we will re approach active Phase 2 participants who a) were ineligible based on previous criteria (protocol v.2.2) when they endorsed “no” to the initial stigma screening question that is no longer used, b) missed their 3-month interview and were not invited to complete a stigma interview, as this was the only visit that was initially approved for scheduling the interview. This interview will be initially offered at the 3-Month time point, but participants may complete it at any point after that until they are no longer in the study.

6.2.8. Newsletter.

In order to give participants a voice and enhance retention, we may create a newsletter 2-3 times per year. The newsletter will include contributions from yoga teachers and study investigators, and anonymous contributions from study participants. Staff will review participant contributions to ensure that they do not include personal identifiers or other information that could clearly identify the participant. Contributions may be short essays, poems, news updates, or pictures. Newsletters will be reviewed by project coordinators, Co-Is, and MPIs before being finalized. When we produce a newsletter, we will have it available for all sites from which we recruit participants. If we have permission to contact participants electronically, we will send them an electronic link to the newsletter via text or email.

6.2.9. Raffle for completing follow-up assessments.

The study statistician will create 3 lists of random numbers such that when a person qualifies for entry into the “raffle,” their ID number will be entered onto the list to determine if they are randomly selected to receive the bonus payment. Approximately 1 in 10 people will receive the bonus payment.

